### **8.2.5.2 Statistical Methods for Safety Analyses**

Safety and tolerability will be assessed by clinical review of all relevant parameters including adverse experiences (AEs), laboratory tests, vital signs, and ECG measurements.

Summary statistics (counts, percentage, mean, standard deviation, etc) will be provided for the safety endpoints as appropriate. The 80% confidence interval for the incidence rate of Grade 2 or higher adverse events with an immune etiology and the incidence rate of Grade 4/5 AEs will be provided as appropriate.

### **8.2.5.3 Summaries of Baseline Characteristics, Demographics, and Other Analyses**

Baseline characteristics will be assessed by the use of tables and/or graphs. No statistical hypothesis tests will be performed on these characteristics. The number and percentage of subjects screened, randomized, the primary reasons for screening failure, and the primary reason for discontinuation will be displayed. Demographic variables (e.g., age, gender), baseline characteristics, primary and secondary diagnoses, and prior and concomitant therapies will be summarized either by descriptive statistics or categorical tables.

### **8.2.5.4 Statistical Methods for Immunogenicity/pharmacokinetics endpoints Analyses**

Summary statistics (mean, standard deviation and range) will be provided for pharmacokinetics measures of MK-3475 and appropriate plots will be generated on pharmacokinetic profiles.

Summary statistics will also be provided for anti-MK-3475 antibody.

### **8.2.6 Multiplicity**

The false positive rate for testing the primary efficacy endpoint is controlled at 0.025 (1-sided). No additional multiplicity adjustment is required.

### **8.2.7 Sample Size and Power Calculations**

In this study, approximately total 35 subjects with advanced melanoma will be enrolled, among them at least 28 from cutaneous melanoma and at most 7 from mucosal melanoma. The 28 cutaneous melanoma subjects are the main analysis population. 7 subjects with mucosal melanoma are population for exploratory analysis.

With approximately 28 evaluable subjects with cutaneous melanoma, the study has approximately 90% power to detect a 25% difference in ORR under the null hypothesis of ORR=10% with a type I error rate of 2.5% if the true ORR is 35%. The null hypothesis rate of 10% is based on the historic response rate in large phase III trials for standard single agent chemotherapy in melanoma [21-30]. Success for this hypothesis requires at least 7/28 responses. The actual number of subjects enrolled may be larger than 28 to ensure that at least 28 subjects are evaluable for primary analysis.

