### **5.9 Subject Replacement Strategy**

A subject who discontinues from the trial will not be replaced.

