#### **8.1.1 Efficacy Analyses**

The full analysis set (FAS) population (defined as all subjects with a baseline scan with measurable disease and who either have a post baseline scan or discontinue the trial due to progressive disease or a drug-related AE) will serve as the primary population for the analyses of efficacy data in this trial. Overall response rate based on RECIST 1.1 will be used as the primary endpoint for efficacy assessment. A 95% confidence interval along with a one-sided p-value for testing the null hypothesis (ORR=10%) based on the binomial distribution will be provided for the response rate. The study is considered to have reached the efficacy objective if the corresponding p-value for testing the respective null hypothesis is less than 2.5%. An outline of the efficacy analysis strategy is presented in [Table 8](#) below.

Table 8 Primary Analysis Strategy for Efficacy Endpoints

Endpoint/Variable (Description, Time Point)	Statistical Method	Analysis Population	Missing Data Approach
Primary:			
Overall RECIST 1.1 response rate based on central radiology review	Exact test of binomial parameter	FAS	Subjects with missing data are considered non-responders
Secondary:			
Overall RECIST 1.1 response rate based on site assessment	Exact methods for binomial parameter	FAS	Subjects with missing data are considered non-responders
Progression-free survival (RECIST 1.1)	Summary statistics using Kaplan-Meier method	FAS	Censored at last assessment
Response duration (RECIST 1.1)	Summary statistics using Kaplan-Meier method	All responders	Non-responders are excluded in analysis
Overall survival	Summary statistics using Kaplan-Meier method	FAS	Censored at last assessment
Overall irRC response rate based on central radiology review	Exact methods for binomial parameter	FAS	Subjects with missing data are considered non-responders
Progression-free survival (irRC)	Summary statistics using Kaplan-Meier method	FAS	Censored at last assessment
Response duration (irRC)	Summary statistics using Kaplan-Meier method	All responders	Non-responders are excluded in analysis

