### 8.1.3 Power and Sample Size

In this study, approximately total 35 subjects with advanced melanoma will be enrolled, among them at least 28 from cutaneous melanoma and at most 7 from mucosal melanoma. The at least 28 cutaneous melanoma subjects are the main analysis population. At most 7 subjects with mucosal melanoma are population for exploratory analysis.

With approximately 28 evaluable subjects with advanced cutaneous melanoma, the study has approximately 90% power to detect a 25% difference in ORR under the null hypothesis of ORR=10% with a type I error rate of 2.5% if the true ORR is 35%. Success for this hypothesis requires at least 7/28 responses. The actual number of subjects enrolled may be larger than 28 to ensure that at least 28 subjects are evaluable for main analysis.

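### The success count that triggers filing is given only for 28 cutaneous subjects, although about 28 to 35 are allowed, and no reading of 7/28 agrees with the exact p<0.025 rule at every permitted size

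*Combined protocol and SAP*

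**What the plan says.** Sections 8.1.3 and 8.2.7 plan about 35 subjects, with 28 or more cutaneous and no more than 7 mucosal. The cutaneous subjects carry the main efficacy analysis. Section 8.2.7 makes 28 a floor: "The actual number of subjects enrolled may be larger than 28 to ensure that at least 28 subjects are evaluable for primary analysis". Section 8.1.3 likewise refers to at least 28 in the main analysis population, while 8.2.7 elsewhere refers simply to the 28.

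Power is stated as about 90% for about 28 evaluable cutaneous subjects, with a null ORR of 10%, a true ORR of 35% and a type I error of 2.5%. Sections 8.1.3 and 8.2.7 both add: "Success for this hypothesis requires at least 7/28 responses". Section 8.2.9 ties the declaration of a positive trial and the preparation for filing to a count over 28 as well, there worded as exceeding 7 rather than reaching it.

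The formal criterion stands in Section 8.1.1: "The study is considered to have reached the efficacy objective if the corresponding p-value for testing the respective null hypothesis is less than 2.5" percent. The test is exact binomial against ORR=10% (8.1.1, 8.2.5.1), and Section 8.2.6 sets the level at 0.025 one-sided. No section gives a count or a power figure for any denominator other than 28, or says whether the count or the p-value prevails if they differ.

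**The concern.** The plan has two success criteria. The p-value adapts to the number of subjects analysed. The count is tied to 28, yet the plan expects that more than 28 may be enrolled. The mucosal figure of 7 is a cap and not a quota, so a larger cutaneous group needs no protocol deviation. It arises whenever fewer than 7 mucosal subjects enrol.

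The sentence in 8.2.9 that leads to filing uses the count and does not mention the p-value. If 30 or more cutaneous subjects were analysed and 7 responded, one section could be read as success and another as failure. Applying a bare 7 at those sizes would also take the one-sided error above the 0.025 that 8.2.6 says is controlled. The issue remains after mucosal subjects are left out of the analysis. Correcting 8.2.9 to match the wording of 8.1.3 and 8.2.7 does not remove it either.

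**Working it through.** **Inputs.** Null ORR 10% and true ORR 35% (8.2.7); one-sided level 0.025 (8.2.6); exact binomial test (8.1.1, 8.2.5.1); success count 7/28 (8.1.3, 8.2.7).

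**Permitted cutaneous n.** With a total of 35 and m mucosal subjects, n = 35 − m, where m runs from 0 to 7. So n runs from 28 to 35.

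**Formula.** P(X ≥ c | n, p) = sum over k = c to n of C(n,k) p^k (1−p)^(n−k). The p-value for c responses uses p = 0.10. Power uses p = 0.35 and the smallest c with p-value below 0.025.

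**The plan's own figure.** For n=28 and c=7, the type I error is 0.0179 and power is 0.9077. The stated figure of about 90% is reproduced.

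**Other sizes.** The last column reads 7/28 as a proportion of at least 25%, that is, 0.25n rounded up.

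| n | p for 7 responses | p for 8 responses | Count needed for p<0.025 | Power at 35% with that count | Count if 7/28 means 25% |
|---|---|---|---|---|---|
| 28 | 0.018 | 0.005 | 7 | 90.8% | 7 |
| 29 | 0.022 | 0.006 | 7 | 92.6% | 8 |
| 30 | 0.026 | 0.008 | 8 | 87.6% | 8 |
| 31 | 0.031 | 0.010 | 8 | 89.9% | 8 |
| 32 | 0.036 | 0.012 | 8 | 91.8% | 8 |
| 33 | 0.042 | 0.014 | 8 | 93.4% | 9 |
| 34 | 0.048 | 0.017 | 8 | 94.7% | 9 |
| 35 | 0.055 | 0.020 | 8 | 95.8% | 9 |
| 36 | 0.063 | 0.024 | 8 | 96.7% | 9 |

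At n=37, 8 responses give p=0.027, so the count of 8 serves only up to n=36.

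**Each reading against the p-value rule, n=28 to 35.**

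- A count of 7 agrees at 28 and 29 and is too lenient at 30 to 35.
- A proportion of at least 25% agrees at 28 and at 30 to 32. It is too strict at 29 (8 required, 7 suffices) and at 33 to 35 (9 required, 8 suffices).
- The 8.2.9 wording, taken as 8 or more responses, agrees at 30 to 35 and is too strict at 28 and 29. At n=28 it has type I error 0.50% and power 81.8%.

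**The case against.** The strongest reply is that the plan already holds the right rule. Every count is written with its denominator of 28, and no section says that 7 is enough at any other size. The criterion in 8.1.1 and the control in 8.2.6 are in terms of the p-value, which adapts to n. The plan's one power figure reproduces, so nothing has been miscalculated. If the 8.2.9 wording were adopted as 8 or more, p would stay below 0.025 at every n from 28 to 35.

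Most of this stands, and it rules out some stronger readings.

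- A reader might infer that the plan fixes success at 7 whatever the n, and so has a type I error of up to 5.5%. The text does not support that. The excess arises only if someone carries the 7 to 30 or more subjects, against 8.1.1 and 8.2.6.
- A reader might infer that over-enrolment costs power. One extra subject raises it, from 90.8% to 92.6%. The fall to 87.6% at n=30 is a discreteness effect under the 8-response rule, 2.4 points below a figure stated as approximate. Power is back to 89.9% at 31 and exceeds the n=28 value from 32. With 7 responses at n=30, power would be 94.1% and type I error 2.58%, so the 87.6% must not be paired with a count of 7.
- A reader might see a contradiction with Section 5.9: "A subject who discontinues from the trial will not be replaced". Planned over-enrolment does not replace subjects who discontinue, and the two provisions are compatible.

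What the reply leaves unanswered is that the filing sentence rests on the count, that the count is undefined beyond 28, and that nothing gives the p-value precedence. Adopting 8 or more would remove the excess error but would depart from the formal test at 28 and 29.

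**Conclusion.** The point holds as a gap in the decision rule. The success count is defined at one size out of a permitted range of about eight, and no reading of it matches the plan's formal test across that range. The practical consequence is confined to borderline results: exactly 7 responses at n=29 to 35, exactly 8 at n=33 to 35 under the 25% reading, and exactly 7 at n=28 or 29 under the 8.2.9 wording. If 7 were wrongly applied as a bare count, the one-sided error would be 2.6% at n=30, rising to 5.5% at n=35.

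This rests on two assumptions: that total enrolment is close to 35, and that all cutaneous subjects in the FAS are analysed. It does not show that the planned test is invalid or that the trial is underpowered. The sample size calculation is sound at n=28.

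**What to change.** In Sections 8.1.3, 8.2.7 and 8.2.9:

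1. Replace the stand-alone count with a statement that exact one-sided p<0.025, at the actual number of cutaneous FAS subjects, governs the declaration of success. Add that this means at least 7 responses for n=28 or 29 and at least 8 for n=30 to 36. The same sentence in 8.2.9 also removes its differing wording of the threshold.
2. State that power at a true ORR of 35% is 90.8% at n=28 and ranges from 87.6% (n=30) to 95.8% (n=35) over n=28 to 35.
3. State that over-enrolled cutaneous subjects who meet the FAS definition stay in the denominator. It should not promise that nobody is excluded, because 8.2.4.1 itself excludes subjects without a dose or without required baseline data. Sections 8.1.1 and 8.2.4.1 define the FAS differently, so the sentence should name the definition that applies.

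The cost is wording only, with no added subjects and no change to the test. The required count is 8 if 30 to 36 cutaneous subjects are in the FAS, which the formal criterion in 8.1.1 already implies.

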### **8.2.8 Subgroup Analyses and Effect of Baseline Factors**

Same efficacy and safety analysis will be conducted on PD-L1 positive subjects and PD-L1 negative subjects, respectively.

Efficacy and safety analysis will also be conducted on BRAF, NRAS, and c-KIT mutation status.

Although the main target population in this study is subjects with advanced cutaneous melanoma, same efficacy and safety analysis will be conducted on subjects with advanced mucosal melanoma exploratory.

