### 3.3 Exploratory Objectives

- 1) **Objective:** To evaluate the efficacy (ORR, DOR, and PFS) per RECIST 1.1 and irRC assessed by the central independent radiology review and OS in subjects with advanced mucosal melanoma receiving MK-3475.
- 2) **Objective:** To explore the PK profile of MK-3475 in the advanced melanoma population.
- 3) **Objective:** To evaluate the presence of anti-MK-3475 antibodies.
- 4) **Objective:** To evaluate the pulmonary radiographic changes and its features for a diagnosis of MK-3475-induced pneumonitis.
- 5) **Objective:** To investigate the correlation between candidate biomarkers (including PD-L1 expression) and anti-tumor activity of MK-3475 in subjects with advanced melanoma.

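### For PD-L1, Section 8.2.8 repeats the one-sample test against 10% in each subset and plans no comparison between subsets, although exploratory objective 5 asks about association

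*Combined protocol and SAP*

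**What the plan says.** Exploratory objective 5 in Section 3.3 reads: "To investigate the correlation between candidate biomarkers (including PD-L1 expression) and anti-tumor activity of MK-3475 in subjects with advanced melanoma". Sections 2.1 and 7.1.3.7 call PD-L1 a pre-defined subgroup analysis in which positive and negative subjects are both evaluated.

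The analysis for it is one sentence in Section 8.2.8: "Same efficacy and safety analysis will be conducted on PD-L1 positive subjects and PD-L1 negative subjects, respectively". Sections 8.1.1 and 8.2.5.1 define the efficacy analysis. For centrally reviewed ORR it consists of a point estimate, a 95% confidence interval and a one-sided exact binomial p-value against 10%. Section 8.2.7 takes that 10% from historical single-agent chemotherapy trials. Tables 8 and 9 add site-assessed and irRC response rates by exact methods, and Kaplan-Meier summaries of PFS, duration of response and OS.

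For BRAF, NRAS and c-KIT, Section 8.2.8 says only that efficacy and safety analysis will also be done by mutation status. No method is named.

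Section 8.2.6 controls the one-sided 0.025 error rate for the primary efficacy endpoint and adds: "No additional multiplicity adjustment is required". Section 8 contains no between-subset contrast, interaction or association measure, gives no expected PD-L1 split, and does not say whether the PD-L1 analysis covers the cutaneous subjects or everyone enrolled.

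**The concern.** An objective about correlation asks whether response differs by marker status. A test of each subset against a chemotherapy benchmark asks something else: whether that subset beats 10%. Both subsets can beat 10% and differ widely, or have the same response rate and receive opposite verdicts because one or both tests have low power.

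Opposite verdicts invite the reading that the drug is active in PD-L1 positive subjects and not in PD-L1 negative ones. If that pattern is common when there is no difference at all, the p-values in the subgroup table add noise to the question that objective 5 poses. The plan contains no figure that would correct the impression.

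**Working it through.** **Inputs.** From Sections 8.2.6 and 8.2.7: null ORR 10%, design ORR 35%, one-sided alpha 0.025, 28 evaluable cutaneous subjects. From Section 4.1.1: ORR of 41% in melanoma, and more than 40% in subjects without prior ipilimumab, which is the population that Section 5.1.3 admits. I therefore also use 41%, and 45% as an assumed higher value. The PD-L1 split is not given; I assume 14/14, 17/11, 20/8 and 21/7.

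**The plan's own figure.** "Success for this hypothesis requires at least 7/28 responses". With X ~ Binomial(28, p): P(X ≥ 7 | 10%) = 0.018 and P(X ≥ 6 | 10%) = 0.055, so 7 is the right threshold. P(X ≥ 7 | 35%) = 90.8%, which agrees with the statement "With approximately 28 evaluable subjects with cutaneous melanoma, the study has approximately 90% power".

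**Thresholds in a subset.** The threshold is the smallest r with P(X ≥ r | n, 10%) ≤ 0.025; power is P(X ≥ r | n, ORR).

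| n | r | Power at 35% | at 41% | at 45% |
|---|---|---|---|---|
| 7 | 4 | 20% | 31% | 39% |
| 8 | 4 | 29% | 43% | 52% |
| 11 | 4 | 57% | 73% | 81% |
| 14 | 5 | 58% | 75% | 83% |
| 17 | 5 | 77% | 89% | 94% |
| 20 | 6 | 75% | 89% | 94% |
| 21 | 6 | 80% | 92% | 96% |

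**Chance that exactly one subset passes when the true ORR is the same in both.** With powers a and b, this is a(1 − b) + b(1 − a). For 14/14 at 35%: 2 × 0.577 × 0.423 = 0.488. For 20/8 at 35%: 0.755 × 0.706 + 0.294 × 0.245 = 0.605.

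| Split of 28 | ORR 35% | ORR 41% | ORR 45% |
|---|---|---|---|
| 14/14 | 48.8% | 37.9% | 27.8% |
| 17/11 | 46.1% | 32.3% | 22.8% |
| 20/8 | 60.5% | 55.5% | 48.0% |
| 21/7 | 68.0% | 66.0% | 60.0% |

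If all 35 subjects are used, at ORR 35%, the figure is 42.3% (18/17), 45.4% (21/14), 45.7% (24/11), 57.8% (26/9) and 74.5% (28/7).

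**One concrete table.** Responses in 7/20 (35.0%) give P(X ≥ 7 | 20, 10%) = 0.0024, a pass. Responses in 3/8 (37.5%) give P(X ≥ 3 | 8, 10%) = 0.038, a fail. The subset with the higher observed rate fails. The difference is −2.5 points, with a Newcombe 95% CI from −39 to +30.

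**What a direct comparison would do.** A two-sided 5% Fisher test between subsets, at a common ORR of 35%, declares a difference in 2.1% (14/14), 2.8% (17/11) and 2.8% (20/8) of trials. Its power for 50% versus 10% is 54%, 56% and 43%. At 14/14 and 35%, the Wald half-width for the difference is 1.96 × √(2 × 0.35 × 0.65 / 14) = 0.35, or about ±35 points.

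**The case against.** Most of the defence stands.

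- A reader might infer that PD-L1 is analysed by nothing but a test, or that the plan cannot address objective 5. That goes too far. The repeated analysis also yields ORR with a 95% CI and Kaplan-Meier summaries in each subset, so the subsets can be set side by side and the difference in rates worked out by subtraction. What is missing is a stated comparison or association measure with its uncertainty.
- A reader might extend the point to BRAF, NRAS and c-KIT. Section 8.2.8 does not say that those analyses repeat the primary one. The method is left open, and a test against 10% there would be conjecture.
- Mucosal melanoma is not a further instance. Its objective in Section 3.3 is to evaluate efficacy in that one group, and a one-sample analysis fits it.
- Low power, and not unequal size alone, drives the discordance: an even 14/14 split already gives 49% at ORR 35%. A contrast does not cure low power.
- No planned inference is wrong. The 2.5% criterion belongs to the primary endpoint, the filing decision in Section 8.2.9 rests on responses out of 28, and objective 5 is exploratory. The absence of a multiplicity adjustment for it is not a fault.

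What the defence does not answer is why a p-value against a chemotherapy rate should appear in a marker analysis at all, or why the quantity that the objective names has no estimator.

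**Conclusion.** The point holds as a cheap improvement to an exploratory analysis. For PD-L1, the plan prescribes a p-value that does not address objective 5 and omits the contrast that would.

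With 28 cutaneous subjects, no true difference between subsets, and splits from 14/14 to 21/7, exactly one subset passes against 10% in 46% to 68% of trials at ORR 35%, and in 23% to 66% at ORR 41% to 45%. It is tempting to summarise this as about half of trials. The documents do not support a single figure, because they give no PD-L1 split and their own background data point to an ORR above the design value.

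The consequence is a risk of misreading. The primary test, its error rate and the filing rule are unaffected.

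**What to change.** In Section 8.2.8, for PD-L1:

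- report ORR with an exact 95% CI in each subset, without a p-value against 10%;
- add the between-subset difference in ORR, or the odds ratio, with a 95% CI;
- state whether the population is the cutaneous subjects or all subjects. Objective 5 speaks of advanced melanoma as a whole, while Section 8.2.7 makes the cutaneous subjects the main analysis population.

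Use the same estimate-and-contrast format for BRAF, NRAS and c-KIT, so that those analyses have a stated method.

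The cost is a few lines of SAP text and a few rows of output, with no new data. There will be fewer p-values to quote, and the contrast will be wide, about ±35 points at 14/14. The interval shows that imprecision openly, which a pair of pass/fail verdicts does not.

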### **8.2.9 Interim Analyses**

No efficacy interim analyses are planned in this trial.

The analysis conducted at the time when all patients are enrolled and have either discontinued or have at least 24 weeks of follow-up since first dose is the main analysis time, if more than 7 /28 responses observed at that time, the trial will declare positive and team will prepare for filing. After the main analysis, the study still follows patients for a longer period of time for duration of response and OS.

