### **8.2.5 Statistical Methods**

Statistical testing and inference for safety analyses are described in 8.2.5.2. Efficacy results that will be considered to be statistically significant after consideration of the strategy for controlling the Type I error are described in Section 8.2.6, Multiplicity. Unless otherwise stated, all statistical tests will be conducted at the  $\alpha=0.05$  (2-sided) level.

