### 8.2.5.1 Statistical Methods for Efficacy Analyses

For the primary efficacy endpoint centrally reviewed RECIST 1.1 response rate, the point estimate, 95% confidence interval, and p-value for testing the RECIST 1.1 response rate is greater than the historical control will be provided using exact binomial distribution. Subjects in the primary analysis population (FAS) without response data will be counted as non-responder.

Secondary efficacy evaluations of RECIST 1.1 response based on investigator assessment will also be conducted using the same methodology as for the primary efficacy analysis.

For PFS endpoint, Kaplan-Meier (KM) curves and median estimates from the KM curves will be provided as appropriate. Subjects without efficacy evaluation data or without survival data will be censored at Day 1. [Table 9](#) summarizes the key efficacy analyses.

Table 9 Analysis Strategy for Key Efficacy Variables

Endpoint/Variable ‡ (Description, Time Point)	Primary vs. Supportive Approach †	Statistical Method	Analysis Population	Missing Data Approach
Primary Hypothesis #1				
Overall RECIST 1.1 response by central radiology assessment	P	Exact test of binomial parameter	FAS	Subjects with missing data are considered non-responders
Secondary Hypothesis #1				
Overall RECIST 1.1 response rate based on site assessment	P	Exact methods for binomial parameter	FAS	Subjects with missing data are considered non-responders
Progression-free survival (RECIST 1.1)	P	Summary statistics using Kaplan-Meier method	FAS	Censored at last assessment
Response duration (RECIST 1.1)	P	Summary statistics using Kaplan-Meier method	All responders	Non-responders are excluded in analysis
Overall survival	P	Summary statistics using Kaplan-Meier method	FAS	Censored at last assessment
Overall irRC response rate based on central radiology review	P	Exact methods for binomial parameter	FAS	Subjects with missing data are considered non-responders
Progression-free survival (irRC)	P	Summary statistics using Kaplan-Meier method	FAS	Censored at last assessment
Response duration (irRC)	P	Summary statistics using Kaplan-Meier method	All responders	Non-responders are excluded in analysis

† P=Primary approach; S=Secondary approach.

The strategy to address multiplicity issues with regard to multiple efficacy endpoints is described in Section 8.2.6, Multiplicity and Section 8.2.9, Interim Analyses.

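### Section 8.2.9 sets the positive declaration at 8 or more responses of 28, while Sections 8.1.3 and 8.2.7 set success at 7 or more; nothing says which rule governs at exactly 7/28

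*Combined protocol and SAP*

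**What the plan says.** The primary efficacy hypothesis concerns centrally reviewed RECIST 1.1 response rate in cutaneous melanoma. The plan states the rule for success in three ways.

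- **By p-value.** Section 8.1.1: "The study is considered to have reached the efficacy objective if the corresponding p-value for testing the respective null hypothesis is less than 2.5" percent. Section 8.2.5.1 specifies the test: "p-value for testing the RECIST 1.1 response rate is greater than the historical control will be provided using exact binomial distribution". Section 8.2.6 fixes the level at 0.025 one-sided, and Section 8.2.5 refers to 8.2.6 for what counts as significant.
- **By count, in the sample size sections.** Section 8.2.7: "Success for this hypothesis requires at least 7/28 responses". Section 8.1.3 has the same sentence. Both attach it to a power statement: "With approximately 28 evaluable subjects with cutaneous melanoma, the study has approximately 90% power to detect a 25% difference in ORR". The null rate there is 10%, the level 2.5% and the assumed true rate 35%.
- **By count, at the main analysis.** Section 8.2.9 first fixes the timing of that analysis and then says "if more than 7 /28 responses observed at that time, the trial will declare positive". Preparation for filing follows from the same condition.

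Section 8.1 calls itself a brief summary and leaves the full detail to Section 8.2. Sections 8.2.7 and 8.2.9 both lie within 8.2, and neither is given precedence.

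**The concern.** More than 7 of 28 means at least 8, so the two count rules differ by one response. A result of exactly 7/28 would meet the efficacy objective under 8.1.1, 8.1.3 and 8.2.7 but would not reach the trigger in 8.2.9. That trigger is the plan's only sentence linking a positive declaration, and the move to filing, to a result at the main analysis.

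This is the decision threshold for the only hypothesis with type I error control. The trial is single-arm and open-label. If 7 responses were seen, the sponsor would have to choose between two written rules with the result in hand. The threshold should be settled before then.

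**Working it through.** **Inputs.** Null rate 10%, alternative 35%, n = 28 evaluable cutaneous subjects and stated power of about 90% (Section 8.2.7); level 0.025 one-sided (Section 8.2.6); exact binomial test (Section 8.2.5.1 and Table 9).

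**Formula.** For a cut-off of k responses, P(X ≥ k | n, p) = Σ from j = k to n of C(n, j) p^j (1 − p)^(n − j). At p = 0.10 this is both the one-sided p-value at k responses and the type I error of the rule. At p = 0.35 it is the power.

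**Step 1: reproduce the plan's figures and compare cut-offs at n = 28.**

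| Cut-off | Type I error (p-value at that count) | Power at 35% |
|---|---|---|
| 6 or more | 0.0550 | 0.9607 |
| 7 or more (8.1.3, 8.2.7) | 0.0179 | 0.9077 |
| 8 or more (8.2.9) | 0.0050 | 0.8179 |

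Six responses fail the 0.025 level and seven pass, so 7 is the smallest successful count. The stated power of about 90% belongs to the cut-off of 7 (90.8%), not to 8 (81.8%).

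**Step 2: confidence interval at 7/28.** The observed rate is 7/28 = 25.0%. The Clopper-Pearson 95% limits are the 0.025 quantile of Beta(7, 22) and the 0.975 quantile of Beta(8, 21), that is 10.7% and 44.9%. The interval excludes 10%, in agreement with the test. At 6/28 it is 8.3% to 41.0% and includes 10%.

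**Step 3: how often the rules disagree.** They differ only when X = 7, with probability C(28, 7) p^7 (1 − p)^21.

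- p = 0.35: 0.0897, which is the difference in power between the two cut-offs (0.90765 − 0.81791, to rounding).
- p = 0.10: 0.0130, which is the difference in type I error (0.01791 − 0.00495).
- The maximum over p is at p = 7/28 = 0.25, where it is 0.1719.

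**Step 4: whether a fixed count carries over to other n.** Section 8.2.7 plans for approximately 28 evaluable subjects and allows enrolment above 28. The smallest count with one-sided p below 0.025 against 10% is:

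| n | Responses needed | Exact p at that count |
|---|---|---|
| 24 to 29 | 7 | 0.0075 (n = 24) to 0.0216 (n = 29) |
| 30 to 36 | 8 | 0.0078 (n = 30) to 0.0235 (n = 36) |

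At n = 30, seven responses give p = 0.0258 and no longer suffice. A count stated for 28 subjects is therefore an illustration of the p-value rule and cannot replace it.

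**The case against.** The strongest reply is that the documents already determine the answer. Section 8.1.1 defines success for the study by the p-value, Sections 8.2.5, 8.2.5.1 and 8.2.6 fix the test and its level, and 7/28 passes. Sections 8.1.3 and 8.2.7 give the same cut-off, and the stated power fits only that cut-off. Section 8.2.9 is then a lone outlier, most likely a slip. It can also be read as a sufficient condition: it says what follows from more than 7 responses, not that 7 responses fail. The error is conservative, and the reported estimate, interval and p-value would be the same under either wording. The disputed outcome becomes less likely if the drug does better than the design rate: 4.3% at a true rate of 40%.

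Most of this stands. Seven is very probably the intended cut-off, there is no threat to type I error, and the 17.2% maximum arises at a true rate that is neither the null nor the design value. It does not remove the conflict. Section 8.1.1 sits in a summary that defers to 8.2, where 8.2.7 and 8.2.9 differ and neither is ranked above the other. If 8.2.9 is only a sufficient condition, it says nothing at exactly 7/28 about the declaration it exists to govern.

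**Conclusion.** The concern holds. Section 8.2.9 is wrong as written: its threshold is one response higher than that in Sections 8.1.3 and 8.2.7, and one higher than the exact test requires at n = 28. This is a conflict of wording, since the plan's cut-off of 7, its type I error limit and its power of about 90% all reproduce.

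The effect is confined to a result of exactly 7/28, with probability 9.0% if the true rate is 35% and 1.3% if it is 10%. Under the documented test at 0.025, power stays at 90.8% and type I error at 1.8%. Only if 8.2.9 were applied as the governing rule would these become 81.8% and 0.5%. The figures assume exactly 28 evaluable cutaneous subjects with independent responses at a common rate.

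**What to change.** In Section 8.2.9, replace the count condition with 7 or more responses of 28. Add a sentence that the exact one-sided test at 0.025 in Section 8.1.1, applied to the number of cutaneous subjects actually analysed, decides success, and that 7/28 is the cut-off it gives at n = 28.

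If 8 or more is truly intended, change Sections 8.1.3 and 8.2.7 to match, align the p-value rule in 8.1.1 with that threshold, and restate power as about 82% and type I error as 0.5%.

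Optionally, list the cut-offs for other sample sizes: 7 for n = 24 to 29 and 8 for n = 30 to 36.

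The cost is an edit to the SAP text, with no additional patients or data. It should be made before the main analysis results are known.
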